A Single-center, Randomized, Open-label Phase Ib/IIa Clinical Study to Evaluate the Safety, Tolerability, Pharmacokinetics, and Preliminary Efficacy of Helicobacter Pylori Eradication after Multiple Doses of TNP-2198 Capsules Combined with Rabeprazole Sodium Enteric-Coated Tablets, and Multiple Doses of TNP-2198 Capsules Combined with Rabeprazole Sodium Enteric-Coated Tablets and Amoxicillin Capsules in Asymptomatic Healthy Participants with Positive Helicobacter Pylori Infection

Protocol Synopsis

Protocol No.: TNP-2198-04

Approval Date: 20 June 2021

Protocol Synopsis

Study Title	A Single-center, Randomized, Open-label Phase Ib/IIa Clinical Study to Evaluate the Safety, Tolerability, Pharmacokinetics, and Preliminary Efficacy of Helicobacter Pylori Eradication after Multiple Doses of TNP-2198 Capsules Combined with Rabeprazole Sodium Enteric-Coated Tablets, and Multiple Doses of TNP-2198 Capsules Combined with Rabeprazole Sodium Enteric-Coated Tablets and Amoxicillin Capsules in Asymptomatic Healthy Participants with Positive Helicobacter Pylori Infection
Study Objectives	
Primary Objectives:
 
 1 To evaluate the safety and tolerability of multiple doses of TNP-2198 Capsules combined with Rabeprazole Sodium Enteric-coated Tablets, and multiple doses of TNP-2198 Capsules combined with Rabeprazole Sodium Enteric-coated Tablets and Amoxicillin Capsules in asymptomatic healthy participants with positive Helicobacter pylori infection; 2 To evaluate the pharmacokinetics of multiple doses of TNP-2198 (including major metabolites), rabeprazole, and amoxicillin in each treatment group. 
Secondary Objectives:
 
To evaluate the preliminary efficacy of multiple-dose combination of TNP-2198 Capsules and Rabeprazole Sodium Enteric-coated Tablets and multiple-dose combination of TNP-2198 Capsules, Rabeprazole Sodium Enteric-coated Tablets and Amoxicillin Capsules in the eradication of Helicobacter pylori.

Clinical Study Protocol No.	TNP-2198-04
Sponsor	TenNor Therapeutics
Clinical Trial Notification No.	CXHL1800160/161
Study Facility	Phase I Drug Clinical Study Center of the First Bethune Hospital of Jilin University
Study Phase	Phase Ib/IIa

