	
The study is designed to evaluate the safety, tolerability, and pharmacokinetics of multiple doses of TNP2198 Capsules combined with Rabeprazole Sodium Enteric-coated Tablets, and multiple doses of TNP-2198 Capsules combined with Rabeprazole Sodium Enteric-coated Tablets and Amoxicillin Capsules in asymptomatic healthy participants with positive Helicobacter pylori infection, and to evaluate the preliminary efficacy of each dosage regimen for Helicobacter pylori eradication.
 
A total of 4 treatment groups will be set up in this study and the participants will be randomized at a ratio of 1: 1: 1: 1.
 
 • Group A: TNP-2198 Capsules 200 mg twice daily (BID) + Rabeprazole Sodium Enteric-coated Tablets 20 mg BID (n=10); • Group B: TNP-2198 Capsules 400 mg BID + Rabeprazole Sodium Enteric-coated Tablets 20 mg BID (n=10); • Group C: TNP-2198 Capsules 600 mg BID + Rabeprazole Sodium Enteric-coated Tablets 20 mg BID (n=10); • Group D: TNP-2198 Capsules 400 mg BID + Rabeprazole Sodium Enteric-coated Tablets 20 mg BID + Amoxicillin Capsules 1 g BID (n=10). 
Screening will occur within 14 days of the first dose of study investigational products. All participants will provide informed consent and undergo Screening evaluations to determine their eligibility. Eligible participants will be admitted to the clinical study center on day -1 (the day before dosing, D-1). On Day 1 to Day 14, breakfast and dinner will be completed within 30 minutes prior to dosing, and the investigational products will be administered after meals. On Day 15, breakfast will be completed within 30 minutes prior to dosing, and the last dose will be administered after meals. Pharmacokinetic blood samples will be collected at the time points scheduled in the protocol during the study, and the safety tolerability evaluation and ¹⁴C urea breath test (UBT) will be conducted.
 
All participants will be discharged after completion of the safety and tolerability evaluation on Day 17 and return to the clinical study center for a follow-up UBT test between Days 44 and 50 to evaluate the preliminary efficacy of Helicobacter pylori eradication.

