Statistical Analysis	
Safety and tolerability analysis
 
The analysis of safety and tolerability are mainly based on descriptive statistics. AEs, serious adverse events (SAEs), drug-related AEs and AEs leading to withdrawal from the study are summarized.
 
The number of participants, number of AEs and incidence of all AEs will be tabulated and summarized by treatment group, system organ class and preferred term.
 
The incidence of adverse events (occurring separately in each treatment group, both in 2 groups, or in 3 groups) in each treatment group will be tabulated and described according to CTCAE grade by treatment group.
 
The number of participants, number of AEs and incidence of AEs in each treatment group will be tabulated according to severity and relationship to the investigational product by system organ class and preferred term.
 
The laboratory test results that are normal before the test but abnormal after treatment are described by treatment group.
 
The mean, standard deviation, median, minimum and maximum values of vital signs (blood pressure, respiratory rate, pulse rate and body temperature) and laboratory test before and after administration are calculated according to the treatment group, respectively. If necessary, paired t test or non-parametric test can be used for comparison before and after administration.
 
SAE and suspected unexpected serious adverse reactions (SUSARs) are presented separately.
 
Pharmacokinetic parameter analysis

Plasma concentrations will be summarized descriptively by treatment group and time point, including: arithmetic mean, standard deviation, minimum, median, maximum, geometric mean, coefficient of variation, geometric coefficient of variation. Descriptive analysis will be performed for the pharmacokinetic parameters calculated after the first and last administration by treatment group, including: arithmetic mean, standard deviation, minimum, median, maximum, geometric mean, coefficient of variation, geometric coefficient of variation, etc. In addition, the accumulation index $AUC_{0-\tau,ss}$ (D15)/ $AUC_{0-\tau}$ (D1) is calculated. Mean and individual concentration-time curves are displayed by linear and semi-logarithmic plotting. Analysis of variance or non-parametric test will be performed on pharmacokinetic parameters between each treatment group.

Preliminary analysis of *Helicobacter pylori* eradication

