The preliminary eradication effect analysis will be based on the full analysis set, which is defined as all participants who are randomized and receive at least one dose of investigational product. The preliminary efficacy of *Helicobacter pylori* eradication will be analyzed descriptively by frequency (percentage) of 4 UBT test results (negative or positive) at baseline, on Day 8, Day 16 and Day 44-50 after last dosing in different treatment groups, and inter-group comparison will be performed. Fisher's exact test will be used for inter-group comparison. As an auxiliary analysis, the mean, standard deviation, median, minimum, maximum, and change from baseline will be presented for UBT values. Inter-group comparisons of UBT values will be analyzed using the model of analysis of covariance or mixed-effects model repeated-measures (MMRM) with baseline UBT values as a covariate, treatment group and dose group as a fixed variable. If the model of analysis of covariance was used, the last observation carried forward (LOCF) was used to impute missing values.

There are no clear statistical hypotheses in this study and all statistical tests are exploratory test with a two-sided 5% nominal significance level. The statistical analysis method and plan are detailed in the statistical analysis plan.

Schedule of Activities

Study Procedures		Screening Visit (D-14-D-2)	D-1	D1	D2-14	D15	D16	D17	Follow-up (during D44-50)
Screening	Signing of ICF	X							
	Demographics	X							
	Medical and surgical history	X	X						
	Concomitant medications	X	X	X	X	X	X	X	X
	Chest plain X-ray	X							
	Abdominal Doppler ultrasound (digestive system + urinary system)	X							
	Infectious disease screening (hepatitis B serologic test, hepatitis C core antigen, hepatitis C antibody, HIV antigen/antibody, treponema pallidum antibody)	X							
	Breath alcohol test		X						
	Urine drug screening (morphine, marijuana)		X						
	Blood pregnancy test	X	X					X	
Enrollment	Verification of inclusion and exclusion criteria	X	X						
	Admission		X						
Study treatment administration	Randomization		X						
	Dosing			X	X	X			
	Clinical laboratory tests (blood routine, blood biochemistry, coagulation, urine routine)¹	X	X		X			X	

Safety and tolerability Assessment	Physical examination²	X	X		X			X	
	12-lead ECG³	X	X	X		X		X	
	Vital signs⁴	X	X	X	X	X	X	X	
	Monitoring and recording of adverse events			X	X	X	X	X	X
PK sample collection	Blood sample⁵			X	X	X	X	X	

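### Rabeprazole is dosed identically in all four arms, but its between-arm PK comparison is planned as a generic test with no exposure ratio or confidence interval (optional improvement)

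*Combined protocol and SAP*

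**What the plan says.** All references are to the Combined protocol and SAP, Protocol Synopsis.

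- **Study Objectives.** The second primary objective covers the PK of TNP-2198 and its major metabolites, together with "rabeprazole, and amoxicillin in each treatment group".
- **Study Design.** There are four arms of 10, and "the participants will be randomized at a ratio of 1: 1: 1: 1". TNP-2198 is 200, 400 and 600 mg BID in Groups A, B and C. Group D is the Group B regimen plus amoxicillin 1 g BID. Rabeprazole is 20 mg BID in all four.
- **Pharmacokinetics Sample Collection.** Rabeprazole is a named plasma analyte, with full 12-hour profiles on Day 1 and Day 15.
- **Statistical Analysis, Pharmacokinetic parameter analysis.** Geometric means and geometric CVs are planned within each group. The only between-group inference is: "Analysis of variance or non-parametric test will be performed on pharmacokinetic parameters between each treatment group".
- **Statistical Analysis, closing paragraph.** There are no formal hypotheses, and "all statistical tests are exploratory test with a two-sided 5% nominal significance level". Further detail is deferred to a statistical analysis plan, and the supplied text does not contain that detail.

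**The concern.** One sentence covers analytes that pose different questions. TNP-2198 exposure should differ between A, B and C because the doses differ. Rabeprazole exposure should not, because its dose is constant. A difference in rabeprazole between randomised arms therefore points to an effect of TNP-2198 dose, to an effect of amoxicillin, or to chance. The design can address two specific comparisons: the trend over A, B and C, and D against B. The supplied text names neither and asks for no estimate of size.

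At 10 per arm, a bare p-value above 0.05 does not tell a reader how large a change in rabeprazole exposure remains possible. That matters for interpreting the combination, and the samples already being collected can supply the answer.

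**Working it through.** The documents state no power, variance or target ratio, so there is no planned figure to reproduce. The inputs from the documents are 4 arms, 10 per arm, two-sided 5%. Assumptions: log-normal exposure, all 40 participants evaluable, and a between-participant CV of 30% to 60%, shown as a range because no CV is given.

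**1. What the comparison can exclude**

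SD on the log scale = sqrt(ln(1 + CV²)). Error df = 40 − 4 = 36, and t(0.975, 36) = 2.028. The 95% CI for a ratio of two arms is the estimate times or divided by exp(2.028 × SD × sqrt(2/10)).

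For CV 30%: SD = sqrt(ln 1.09) = 0.294, and exp(2.028 × 0.294 × 0.447) = 1.305.

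| Assumed CV | SD (log) | Factor | 95% CI at an observed ratio of 1.0 |
|---|---|---|---|
| 30% | 0.294 | 1.305 | 0.77 to 1.31 |
| 40% | 0.385 | 1.418 | 0.71 to 1.42 |
| 50% | 0.472 | 1.535 | 0.65 to 1.53 |
| 60% | 0.555 | 1.654 | 0.60 to 1.65 |

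The same widths apply to C/A and to D/B.

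**2. Power, on the omnibus reading**

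Let log exposure rise linearly with dose, with D equal to B, so the log means are −d, 0, +d, 0 and d = ln(C/A)/2. Because the doses are equally spaced, the linear contrast has weights (−1, 0, 1) over A, B and C, so its estimate is the C/A ratio. Both tests then have noncentrality λ = 2 × 10 × d²/SD², with 3 and 36 df for the four-arm ANOVA and 1 and 36 df for the contrast.

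For C/A = 1.5 and CV 40%: d = 0.203, λ = 20 × 0.0411/0.1484 = 5.54.

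| CV, with C/A = 1.5 | Four-arm log-scale ANOVA | Linear contrast |
|---|---|---|
| 30% | 68.7% | 85.2% |
| 40% | 43.8% | 62.9% |
| 50% | 30.1% | 46.3% |
| 60% | 22.5% | 35.6% |

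Over all λ, the largest gap is 19.3 points (68.5% against 49.2%, at λ about 6.3). That corresponds to C/A of about 1.39, 1.54, 1.70 or 1.86 at CV 30%, 40%, 50% or 60%.

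**3. How far that gain depends on the setting**

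- *Kruskal-Wallis instead of ANOVA:* the gap reaches about 23.5 points by simulation.
- *Unadjusted pairwise tests:* C against A with pooled error is the same test as the contrast, so the loss is zero. As a separate two-sample test (18 df) it has 66.1% against 68.5%, about 2 points. If all six pairs are tested unadjusted and no arm differs, the chance of at least one false positive is about 20% per parameter (0.197, studentized range).
- *D against B with only D shifted, or an effect only at the top dose, or a plateau from 400 mg:* the contrast's λ is two thirds of the omnibus λ, and the difference is −1.5 to +3.2 points.
- *A equal to C and B equal to D, but the two pairs different:* the linear contrast has 5% power. The omnibus test is better, for example 60% at an omnibus λ of 8.

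**The case against.** The strongest reply is that this is an exploratory trial with no hypotheses and no stated interaction objective. The second primary objective describes PK within each group. The plan already commits to per-arm geometric means and geometric CVs, from which, with the group sizes, anyone can compute the C/A and D/B ratios and their intervals. The wording about testing between each treatment group can be read as pairwise, in which case C against A and D against B are already included. The missing detail may also sit in the separate statistical analysis plan.

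Most of this stands, and it limits the point to a reporting improvement. It does not remove it. An exploratory comparison benefits more from an estimate with an interval than from a nominal p-value, and the supplied text asks only for the test. If the separate plan already specifies these ratios, the sponsor need only confirm that.

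A reader might infer three stronger things that the documents do not support:

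- *That the plan as written loses 19 points of power.* This needs an omnibus reading, a log-scale ANOVA, a log-linear dose effect, D equal to B and a particular effect-to-SD ratio. The documents establish none of these.
- *That a non-significant result will be reported as no interaction.* Nothing in the text says so.
- *That a change in rabeprazole exposure would invalidate the arm comparisons.* It would not: the secondary objective concerns the combinations, and any such change would be part of the randomised regimen's effect. The contrast would not separate the two drugs' contributions.

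**Conclusion.** The point holds as an optional improvement. The supplied text plans no exposure ratio with an interval for rabeprazole, although its constant dose makes the between-arm comparison an interaction question. At an observed ratio of 1.0 with 10 per arm, exposure from about 31% higher and 23% lower (assumed CV 30%) to about 65% higher and 40% lower (assumed CV 60%) would remain compatible with the data. These figures rest on log-normality, complete data and assumed CVs.

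The fix does not narrow those intervals; it makes them visible. Any power gain is conditional and should not be the reason for the change. The design has no arm on rabeprazole alone, so only a TNP-2198 interaction that varies with dose can be detected. An effect of the same size at 200, 400 and 600 mg would not show.

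**What to change.** For rabeprazole AUC0-tau and Cmax on Day 1, and AUC0-tau,ss and Cmax,ss on Day 15:

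1. Fit one linear model per parameter on the log scale, with the four arms as a factor.
2. Report as the main comparisons the linear dose contrast over A, B and C, expressed as the C/A geometric mean ratio with 95% CI, and the D/B geometric mean ratio with 95% CI.
3. Keep the four-group test as secondary, because the linear contrast has little power for a non-monotone pattern.
4. State that, without a rabeprazole-alone arm, only a dose-dependent TNP-2198 interaction can be detected, and that non-significance is not evidence of no interaction.

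The cost is a few sentences in the analysis plan and a few lines of code. No extra samples, visits or participants are needed.

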	
 • Apparent volume of distribution (V_d/F) • Apparent clearance (CL/F) 
Last dose PK parameters include at least:
 
 • Time to peak ($T_{max,ss}$) • Maximum plasma concentration at steady state ($C_{max,ss}$) • Minimum plasma concentration at steady state ($C_{min,ss}$) • Mean plasma concentration at steady state ($C_{avg,ss}$) • Elimination half-life ($t_{1/2,ss}$) • Area under the plasma concentration-time curve from the last dose to the last measurable concentration time point ($AUC_{0-last, ss}$) • Area under the plasma concentration-time curve from the last dose to the dosing interval (12 h) ($AUC_{0-tau,ss}$) • Area under the plasma concentration-time curve from the last dose extrapolated to infinity ($AUC_{0-infty, ss}$) • Apparent volume of distribution at steady state (V/F_{ss}) • Apparent clearance (CL/F_{ss}) • Accumulation Index (R_{ac}): $AUC_{0-tau,ss}$ on Day 15/AUC_{0-tau} on Day 1 • Fluctuation index (DF): Percentage fluctuation at steady state = $100 \times (C_{max,ss} - C_{min,ss})/C_{avg, ss}$
Preliminary Evaluation of Helicobacter pylori Eradication	
All participants will undergo a total of 4 UBT tests (under fasting conditions before breakfast) at baseline, Day 8, Day 16, and Day 44-50 after last dosing, to evaluate the preliminary efficacy in the eradication of Helicobacter pylori.

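### If UBT values are compared by ANCOVA, the planned LOCF can put a Day 16 or Day 8 result in place of a missing Day 44-50 result; the printed model terms also leave the comparison visit open (minor)

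*Combined protocol and SAP*

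**What the plan says.** All references are to the Protocol Synopsis.

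- **Model.** Under Statistical Analysis (preliminary analysis of eradication), UBT values are compared between groups by one of two models, "using the model of analysis of covariance or mixed-effects model repeated-measures (MMRM"). The same terms are listed for either model: "with baseline UBT values as a covariate, treatment group and dose group as a fixed variable". No rule chooses between the two models. No visit term, covariance structure or comparison visit is given.
- **Missing data.** The next sentence reads: "If the model of analysis of covariance was used, the last observation carried forward (LOCF) was used to impute missing values".
- **Deferral.** The section closes with "The statistical analysis method and plan are detailed in the statistical analysis plan". That plan is not among the documents supplied.
- **Visits.** Under Preliminary Evaluation of Helicobacter pylori Eradication, "All participants will undergo a total of 4 UBT tests": one at baseline and three afterwards (Day 8, Day 16, Day 44-50).
- **Timing.** Under Study Design, "On Day 15, breakfast will be completed within 30 minutes prior to dosing, and the last dose will be administered after meals". Discharge is on Day 17, after which participants "return to the clinical study center for a follow-up UBT test between Days 44 and 50 to evaluate the preliminary efficacy"; the efficacy meant there is eradication.
- **Arms.** "A total of 4 treatment groups will be set up in this study", with 10 participants each.

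**The concern.** The three post-baseline tests describe different states. Day 8 falls during dosing, Day 16 one day after the last dose, and the follow-up test about a month later. The follow-up is also the only one of the three that needs a return visit after discharge, so it is the one most exposed to loss. LOCF would fill that gap with a result taken during treatment or just after it. The completed data set would then treat that result as a follow-up result.

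The term list raises a second, weaker question. One arm effect with no visit interaction does not say which visit the comparison refers to. Two analysts following the sentence could report different quantities from the same data. At stake is whether the reported UBT-value difference describes the follow-up visit at all.

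**Working it through.** The plan states no power, effect size, UBT variance, correlation or dropout rate for this model, so there is no figure of its own to reproduce. The inputs from the documents are 4 arms of 10 (40 participants), three post-baseline visits (40 × 3 = 120 planned values) and the last dose on Day 15. Everything else below is assumed and shown as a range.

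**1. LOCF under ANCOVA at Day 44-50.** Suppose k of 10 in each arm lack the follow-up value for reasons unrelated to outcome and are filled from Day 16. With balanced baselines,

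expected difference = (1 − k/10) × d(44-50) + (k/10) × d(16).

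As a fraction of the Day 44-50 difference:

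| Missing per arm (of 10) | No arm difference at Day 16 | Day 16 difference half as large |
|---|---|---|
| 0 | 1.00 | 1.00 |
| 1 | 0.90 | 0.95 |
| 2 | 0.80 | 0.90 |
| 3 | 0.70 | 0.85 |

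**2. Unequal missingness.** Suppose two arms have the same Day 44-50 mean, 1 unit above their common Day 16 mean. One arm is complete and the other lacks a share m. The LOCF difference is [(1 − m) × 1 + m × 0] − 1 = −m. For m = 0.1 to 0.3, a difference of 0.1 to 0.3 units appears where none exists.

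**3. MMRM fitted literally.** With complete data and no visit interaction, the arm coefficient is a weighted sum of the three visit differences. The weights are V⁻¹1 / (1′V⁻¹1), where V is the within-participant covariance. With SDs of 1, 1 and s and a common correlation, the weight on Day 44-50 is:

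| Day 44-50 SD (s) | Corr. 0 | Corr. 0.3 | Corr. 0.6 |
|---|---|---|---|
| 0.5 | 0.67 | 0.83 | 1.11 |
| 1 | 0.33 | 0.33 | 0.33 |
| 2 | 0.11 | 0.01 | −0.17 |

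A visit main effect alone changes none of these. With arm-by-visit, the Day 44-50 contrast recovers a true difference of 1 as 1.00 in all nine settings. If arm differences are the same at every visit, the weights do not matter, because they sum to 1.

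**4. Baseline-by-visit.** With assumed baseline slopes of 0.8, 0.4 and 0 at the three visits, 10 per arm, unit SDs and noise-free outcomes, a model with arm-by-visit but one common baseline slope gives a Day 44-50 contrast that averages about 1.0 over random baselines. Its SD is about 0.16 to 0.18. Adding baseline-by-visit gives 1.000 every time.

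**5. Dose group.** On 40 rows, baseline plus four arms has 5 columns and rank 5. Adding dose gives 7 columns and still rank 5. If treatment group means with or without amoxicillin, then baseline, regimen and dose give 5 columns and rank 5. Either way the four arms are distinguished.

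**6. The follow-up window.** Study Design and the Schedule of Activities give study Days 44 to 50, which is 44 − 15 = 29 to 50 − 15 = 35 days after the last dose. Preliminary Evaluation and Statistical Analysis count Day 44-50 from the last dose, which read literally is study Day 15 + 44 = 59 to 15 + 50 = 65.

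**The case against.** This is one sentence in a synopsis that refers the reader to a SAP for the detail. It covers ANCOVA and MMRM together, so it may list only the terms they share, and a single-visit ANCOVA has no visit term. The text just before it tabulates results at each visit, which makes a per-visit comparison the natural reading. All magnitudes above rest on assumed variances, correlations and missingness. The synopsis also counts all four UBT tests toward preliminary efficacy, the analysis is auxiliary, and no hypothesis depends on it.

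Most of this stands, and it limits the second part of the point. A reader might infer that the planned MMRM is wrong because it cannot estimate the Day 44-50 difference. The documents do not support that: it would require the MMRM to be fitted without the usual visit terms and the arm differences to vary over visits, and the SAP may already list the terms. A reader might also infer that dose group makes the arm comparisons inestimable. It does not; at worst it is redundant, and the matter is one of wording.

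The objection does not remove the LOCF part. LOCF is a stated rule, not an omitted detail, and supplying more detail elsewhere would not change what it does to a missing follow-up value.

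**Conclusion.** The point holds as a minor one. If ANCOVA is chosen and follow-up values are missing, LOCF shifts the expected comparison away from the Day 44-50 difference: to 0.90-0.70 of it with 1-3 of 10 missing per arm, missingness unrelated to outcome and no arm difference at Day 16, or 0.95-0.85 if the Day 16 difference is half as large. Unequal missingness can create a false difference. With complete follow-up there is no effect, and the documents give no missingness rate.

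The missing visit terms are established only for the sentence as printed. Read literally, the MMRM matches the Day 44-50 difference in general only if arm differences are constant over visits.

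It would be too strong to say that the trial's eradication findings are compromised. The negative/positive tables, Fisher's exact test and the descriptive UBT summaries do not use this model, and all tests are exploratory.

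**What to change.** First reconcile the two definitions of the follow-up window (study Days 44-50, or counted from the last dose), so that the comparison visit is fixed. Then make MMRM, which the plan already permits, the single method, and delete the ANCOVA/LOCF option. Suggested text:

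> Inter-group comparisons of UBT values will use an MMRM on all post-baseline UBT values, with arm (A, B, C, D), visit, arm-by-visit, baseline UBT and baseline-by-visit as fixed effects and an unstructured within-participant covariance; [a named simpler structure] will be used if it does not converge. Arm differences with 95% CI will be reported at each visit, with the follow-up visit as the comparison for eradication. Earlier values will not be carried forward to the follow-up visit.

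Naming the four arms in place of treatment group and dose group is a change of wording only. Fisher's test stays as planned. If the SAP already says this, aligning the synopsis is enough.

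**Cost.** A few sentences and standard code, with no new data; the Day 8 and Day 16 comparisons are kept. The model has 1 + 3 + 2 + 6 + 1 + 2 = 15 fixed-effect parameters instead of 5, plus 6 covariance parameters, from 40 participants, hence the stated fallback. If arm differences really are constant over visits, the Day 44-50 standard error is about √(3/(1 + 2 × correlation)) = 1.73, 1.37 or 1.17 times that of the pooled estimate at correlation 0, 0.3 or 0.6 (equal variances). Participants without a follow-up value still contribute through Day 8 or Day 16, but under a missing-at-random assumption.

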Preliminary efficacy of Hp eradication	¹⁴ C-urea breath test ⁶	X	X		X		X		X
End of study	Discharge							X	
	Follow-up, study completion								X

Note:

- 1 Clinical laboratory tests will be performed at the screening period, baseline period, D4, D6, D8, D12 (before the first dose), and D17 (48 h after dosing on D15). The results of screening examination within 7 days can be used for the baseline period, and no additional test will be required.
- 2 Physical examination will be performed at the screening period, baseline period (D-1), D4, D6, D8, D12 and D17.
- 3 12-lead ECG will be performed at the screening period, baseline period (D-1), D1 (2 h after the first dose), D15 (within 60 min before and 2 h after dosing) and D17 (48 h after dosing on D15).
- 4 Vital signs will be examined at the screening period, baseline period (D-1), D1 (within 60 min before the first dose and 0.5 h, 2 h, 4 h, 8 h, 12 h after dosing), D2-14 (within 60 min before the first dose), D15 (within 60 min before dosing and 0.5 h, 2 h, 4 h, 8 h, 12 h after dosing), D16 (24 h after dosing on D15) and D17 (48 h after dosing on D15).
- 5 PK blood samples will be collected on D1 (within 30 min before breakfast, and 0.5 h, 1 h, 1.5 h, 2 h, 2.5 h, 3 h, 3.5 h, 4 h, 5 h, 6 h, 7 h, 8 h, 9 h, 10 h, 11 h, 12 h after dosing), within 30 min before breakfast on D3, D5, D7, D9, D11, D13 and D14, on D15 (within 30 min before breakfast, and 0.5 h, 1 h, 1.5 h, 2 h, 2.5 h, 3 h, 3.5 h, 4 h, 5 h, 6 h, 7 h, 8 h, 9 h, 10 h, 11 h, 12 h after dosing), D16 (24 h after dosing on D15) and D17 (48 h after dosing on D15).
- 6 UBT will be performed in fasting state before breakfast and will be performed on D8 during D2-14; the results of screening examination within 7 days can be used for the baseline period, and no additional test will be required

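### In the auxiliary UBT-value comparison, LOCF under the ANCOVA option can put a Day 16 value, taken about 24 h after the last dose, in place of a missing follow-up value

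*Combined protocol and SAP*

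**What the plan says.** The rule is in the Protocol Synopsis, Statistical Analysis, under the preliminary analysis of *Helicobacter pylori* eradication.

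- **Model.** The choice is left open: "Inter-group comparisons of UBT values will be analyzed using the model of analysis of covariance or mixed-effects model repeated-measures (MMRM". The analysis is labelled auxiliary, and the section declares all tests exploratory at a nominal two-sided 5% level.
- **Missing data.** "If the model of analysis of covariance was used, the last observation carried forward (LOCF) was used to impute missing values". The text sets no limit on which visit may be carried forward, and does not name the visit at which ANCOVA is applied.
- **Analysis set.** Randomization and one dose are enough, so a participant without a follow-up UBT remains in the set.
- **Last dose** (Study Design): "On Day 15, breakfast will be completed within 30 minutes prior to dosing, and the last dose will be administered after meals".
- **UBT conditions** (Schedule of Activities, note 6): "UBT will be performed in fasting state before breakfast and will be performed on D8 during D2-14".
- **Purpose of follow-up** (Study Design): participants "return to the clinical study center for a follow-up UBT test between Days 44 and 50 to evaluate the preliminary efficacy".

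The section refers to a statistical analysis plan for details. The text available is the synopsis and its schedule, so a restriction elsewhere cannot be ruled out.

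**The concern.** The follow-up UBT is the visit that the design assigns to judging eradication, weeks after treatment has stopped. A Day 16 value answers a different question: what the test reads one day after two weeks of dosing. Discharge is on Day 17, so follow-up is the only post-treatment UBT that needs a return visit. Day 16 present with follow-up absent is therefore a natural pattern of missing data, and it is the one in which LOCF makes this substitution. For earlier losses the rule could also carry a Day 8 or baseline value.

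At stake is the model-based comparison of UBT values between dose groups, or with and without amoxicillin. With 10 per arm, each imputed participant is a tenth of the arm.

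**Working it through.** **Timing.** The Dosing Regimen states 29 doses. This reproduces: 14 days x 2 + 1 dose on Day 15 = 29. With a fasting test before breakfast, the Day 16 UBT is 16 - 15 = 1 day after the last dose. Schedule notes 4 and 5 give the same 24 h for vital signs and PK on that day. On study Days 44-50, follow-up is 44 - 15 = 29 to 50 - 15 = 35 days after the last dose, so LOCF would bridge 44 - 16 = 28 to 50 - 16 = 34 days.

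**Inputs not in the documents.** Loss rate, UBT standard deviation and off-treatment rebound are all assumed. If 5%, 10% or 20% miss follow-up, the chance of at least one such loss in an arm of 10 is 1 - 0.95^10 = 40%, 1 - 0.90^10 = 65% or 1 - 0.80^10 = 89%.

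**Shift in one arm.** Take lower values as favourable. With m of 10 carried forward and rebound d, the shift in the arm's follow-up mean is -(m/10) x d. At d = 1 SD and m = 1, 2, 3 this is -0.10, -0.20, -0.30 SD.

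**Bias between arms.** For arm C minus arm A it is -(m_C x d_C - m_A x d_A)/10. With equal rebound, only the net difference in losses counts.

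**Test behaviour.** Simulation of LOCF-ANCOVA: 4 arms of 10, SD 1, correlation 0.5 between visits (assumed), no true difference at follow-up, loss unrelated to outcome.

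| Lost in A/B/C/D | Rebound (SD) | Bias, C minus A (SD) | Rejection at nominal 5% |
|---|---|---|---|
| 0/0/3/0 | 0 | 0.00 | 4.9% |
| 0/0/1/0 | 1 | -0.10 | 5.4% |
| 0/0/2/0 | 1 | -0.20 | 7.1% |
| 0/0/3/0 | 0.5 | -0.15 | 6.5% |
| 0/0/3/0 | 1 | -0.30 | 10.0% |
| 0/0/2/0 | 2 | -0.40 | 12.0% |
| 0/0/3/0 | 2 | -0.60 | 22.6% |
| 1/1/2/1 | 1 | -0.10 | 4.2% |
| 1/1/3/1 | 1 | -0.20 | 5.5-5.7% |
| 1/1/3/1 | 2 | -0.40 | 6.0% |
| 2/2/2/2 | 1 | 0.00 | 3.1% |
| 2/2/2/2 | 2 in C, 0.5 elsewhere | -0.30 | 7.3% |
| Same random loss in all arms (5, 10 or 20%) | 1 or 2 | within 0.003 | 4.7-5.1% |

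Two features explain the table. Bias follows the net imbalance. Rejection does not follow bias alone: losses in every arm mix low carried-forward values with true follow-up values, which widens the within-arm spread and the standard error. Hence 3.1% with two lost in every arm, and barely more than 5% for 1/1/3/1 despite a bias of -0.20 SD.

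With 3 lost in one arm and 1 SD rebound, a correlation of 0.3 or 0.7 gives 9.3% or 12.5% in place of 10.0%. ANCOVA on observed follow-up values had bias near zero and rejected about 5% under the same assumptions.

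**The case against.** The case against treating this as a defect is substantial.

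- **A chain of conditions.** ANCOVA must be chosen over the equally permitted MMRM, follow-up must be the visit analysed, a follow-up value must be missing with Day 16 present, values must rise off treatment, and losses or rebound must differ by arm. The documents settle none of these. This stands, and it is why the point is minor. It does not remove the point, because the visible rule leaves the route open.
- **Detail belongs to the SAP.** The visit and any limit on carry-forward may be set there. This also stands. The criticism is of the rule as written in the text available.
- **The large rejection rates are selective.** They come from layouts with several losses in one arm and none in the others. This stands: equal random loss leaves the test near its nominal level.

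A reader might infer more from the LOCF sentence in three ways, none of which the documents support.

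1. *That eradication rates are inflated.* The negative/positive percentages, Fisher's test and the descriptive UBT summaries carry no LOCF rule.
2. *That the UBT-value test is generally too liberal.* It can be at, above or below 5%, depending on the pattern of loss.
3. *That LOCF is the planned method.* It applies only if ANCOVA is used.

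**Conclusion.** The concern holds in a limited form. In the text available, the ANCOVA option lets a value from about 24 h after the last dose stand in for the off-treatment eradication value, provided that follow-up is the visit analysed, as its stated purpose suggests.

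Given an off-treatment rise in UBT values, the affected arm looks better than it should. The between-arm difference is biased only through unequal losses or unequal rebound: about -0.1 to -0.3 SD for a net imbalance of one to three of 10 at 1 SD rebound. With zero rebound, or with equal random loss and equal rebound, there is no average bias. Among the cases run with correlation 0.5, rejection reached 10% only with two or three losses in one arm, none in the others, and a rebound of at least 1 SD (2 SD when two were lost).

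Severity is minor: the analysis is auxiliary, the objective is secondary and every test is exploratory.

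**What to change.** 1. Delete the LOCF sentence and state that no Day 8 or Day 16 UBT value is carried into the follow-up visit.
2. Name follow-up as the visit for the inter-group comparison of UBT values.
3. Use the already permitted MMRM with baseline UBT value, treatment group, visit and treatment-by-visit, read at follow-up. ANCOVA on observed follow-up values is an acceptable simpler choice.

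**Cost.** Wording only; no new visits or data. There may be a small loss of precision: with 3 missing in one arm and 1 SD rebound, the SD of the between-arm difference is about 0.43 SD for either alternative, against 0.39 SD for LOCF. This does not hold generally. With 20% random loss and 2 SD rebound, LOCF is the less precise (0.54 SD against 0.45 SD for observed-case ANCOVA). Both alternatives rely on missing at random, so bias remains if those lost rebound more than those seen.

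**Separately**, the follow-up visit needs one definition. The eradication evaluation row places the tests "at baseline, Day 8, Day 16, and Day 44-50 after last dosing", and the statistical section has similar wording. Study Design and the schedule header use study Days 44-50. Read literally, the first means study Days 15 + 44 = 59 to 15 + 50 = 65. These passages must be reconciled; the LOCF point holds on either reading.
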